8.3.3 CLASSIFICATION OF AN ADVERSE EVENT

8.3.3.1 SEVERITY OF EVENT

Each AE will be assigned a category by the Investigator as follows:

Mild: An AE that is easily tolerated by the subject, require minimal or no treatment and does not interfere with the participant's daily activities.

Moderate: An AE that results in a low level of inconvenience or concern with the therapeutic measures. Moderate events may cause some interference with functioning. Intervention may be needed.

Severe: An AE that prevents everyday activities and may require systemic drug therapy or other treatment. Severe events are usually potentially life-threatening or incapacitating.

If there is a change in the severity of an AE, it must be recorded as a separate event.

8.3.3.2 RELATIONSHIP TO STUDY INTERVENTION/EXPERIMENTAL MANIPULATION

The investigator will make every effort to assess the relationship of the AE, if any, to the study intervention. The investigator should use their knowledge of the subject, the circumstances surrounding the event, and

an evaluation of any potential alternative causes to determine whether an AE is related to the study treatment. Causality should be assessed using the categories presented below:

Related: The AE is known to occur with the study intervention, there is a reasonable possibility that the study intervention caused the AE, or there is a temporal relationship between the study intervention and event. Reasonable possibility means that there is evidence to suggest a causal relationship between the study intervention and the AE.

Not Related: There is not a reasonable possibility that the administration of the study intervention caused the event, there is no temporal relationship between the study intervention and event onset, or an alternate etiology has been established.

Action Taken

The investigator will describe the action taken in the proper section of the CRF, as follows:

- None
- Study procedure or the medication stopped
- Study medication temporarily interrupted
- Concomitant medication
- Other, specify.

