We will recruit n=20 patients throughout Greater Inland Northwest area. We anticipate a five-month recruitment period, necessitating four recruited per month which is far below our normal recruitment rates. Flyers will advertise the study, and staff and providers will be aware of the study and will be asked to refer potentially interested participants to our investigation. Initial eligibility for a referral will be provided by AUDIT screen and Screen, Brief Intervention, and Referral to Treatment performed at the different treatment centers. Once the treatment center has completed its screening and intervention, they will utilize the AUDIT score to determine the patients that will be provided, the study Research Coordinator contact number for study screening. After an initial phone screening, eligible participants will be scheduled for an in-person study interview, during which they will provide informed consent and complete baseline data collection. During this time, participants will also receive a brief tutorial on how to use the BACtrack breathalyzer and how it integrates with the application on their smartphone. Participants who do not have a compatible iOS smartphone will be provided one for this study. The phones will be supplied from a testing inventory maintained by Managed Health Connections. Participant set-up instructions will also describe the time window for reporting, the definition of zones of use, and will be provided contact information for technical support to be used during the study.

During the A-B-A phase (2-4-2 weeks), participants will be asked to submit three breath samples daily for 8 weeks. They will also be asked to fill out a weekly timeline follow back for alcohol, tobacco, and cannabis use during that period. At the end of the 8 weeks participation period, participants will bring back the phone and fill out the exit questionnaire.

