9.3.4 SAFETY ANALYSES

Medical coding will use MedDRA for the concomitant diseases (Medical History) and AEs and the World Health Organization (WHO) Drug Dictionary for medications.

Each AE will be counted once only for a given participant. The AEs expectedness, severity, frequency, and their relationship to the study intervention will be presented by System Organ Class (SOC) and preferred term groupings. Adverse events leading to premature discontinuation from the study intervention and serious treatment-emergent AEs will be presented either in a table or a listing.

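### The two AE causality categories in section 8.3.3.2 overlap, so the Related/Not Related split depends on which clause the assessor applies

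*Protocol*

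**What the plan says.** Section 8.3.3.2 of the Protocol asks the investigator to draw on knowledge of the subject, the circumstances and "an evaluation of any potential alternative causes to determine whether an AE is related to the study treatment". It then directs that causality be assessed with two categories.

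- **Related** has three alternatives: the event is a recognised effect of the intervention; or causation is reasonably possible; "or there is a temporal relationship between the study intervention and event". The section adds: "Reasonable possibility means that there is evidence to suggest a causal relationship between the study intervention and the AE".
- **Not Related** also has three alternatives: "There is not a reasonable possibility that the administration of the study intervention caused the event", or "there is no temporal relationship between the study intervention and event onset, or an alternate etiology has been established".

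Section 8.3.5 requires a causal judgement and a date of first occurrence for every AE. Section 9.3.4 then tabulates the judgement: AEs and "their relationship to the study intervention will be presented by System Organ Class (SOC) and preferred term groupings".

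On exposure, section 4.1 says that "participants will be asked to submit three breath samples daily for 8 weeks", in phases of 2, 4 and 2 weeks. Payment depends on abstinence only in the middle, 4-week B phase. In both A phases payment is for submitting a sample, whatever the result.

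**The concern.** A two-category scale should place each event in one category. Here the tests for the two categories are not complements of each other. Timing alone admits an event to Related, and a different fact about the same event can admit it to Not Related. Take an infection in week 4 with an established cause outside the study. It can be called Related because it arose while the system was in use, and Not Related because its etiology is established.

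If assessors resolve this differently, or one assessor does so differently over time, the split in the safety table reflects the clause applied as well as the events. The design has no concurrent control group, so no control-arm AE rate is available to offset an inconsistent attribution. The protocol itself has alcohol withdrawal in view: section 5.2 excludes people at significant risk of dangerous withdrawal, and section 8.3.3.3 gives the expectedness decision to a provider with expertise in it. Events of that kind need consistent attribution. An analysis plan could not repair the problem later, because the judgement is made by the investigator when the case report form (CRF) is completed.

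**Working it through.** The plan gives no figure on this point to reproduce. The check is logical: list every combination of the criteria and count those that meet both definitions.

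**Inputs (section 8.3.3.2).** Four yes/no criteria:
- K: the event is a recognised effect of the intervention
- R: there is a reasonable possibility of causation
- T: there is a temporal relationship
- E: an alternate etiology is established

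This gives 2 × 2 × 2 × 2 = 16 combinations.

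**Definitions as printed.**
- Related = K or R or T
- Not Related = (not R) or (not T) or E

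**Count by hand.** Related fails only when K, R and T are all absent, with E either way: 2 combinations, both Not Related only. Not Related fails only when R and T are present and E is absent, with K either way: 2 combinations, both Related only. The remaining 16 − 2 − 2 = 12 meet both, and none meets neither.

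**Within T present** (8 combinations): all 8 are Related. Not Related fails only for R present with E absent, which is 2, so 8 − 2 = 6 meet both. With T and E both present, 4 of 4 meet both.

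**Sensitivity to how the Not Related list is read.**

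| Reading of Not Related | Both, all 16 | Both, T present (of 8) | Both, T and E present (of 4) |
|---|---|---|---|
| All joined by 'or', as printed | 12 | 6 | 4 |
| (not R and not T) or E | 8 | 4 | 4 |
| All three required together | 1 | 0 | 0 |

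Only the third reading removes the overlap when timing is present. It contradicts the printed 'or', leaves 1 combination in neither category, and makes all 8 combinations with T Related even when another cause is established. That sits badly with the instruction to evaluate alternative causes.

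**Exposure.** Daily sampling covers 8 × 7 = 56 days. The contingent phase covers 4 × 7 = 28 days, and 28/56 is half. Section 8.3.3.2 does not say which of these is the study intervention for the causality judgement. Section 8.3.4 records events from consent until 7 days (non-serious) or 30 days (serious) after the last day of participation, so some recorded events fall outside both periods.

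**After the proposed change.** If Related is decided by R and Not Related by its absence, the 16 combinations divide 8 and 8, with none in both and none in neither.

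**The case against.** The strongest reply is that causality is a clinical judgement, not a truth table. The section tells the investigator to weigh alternative causes before assigning a category, which points towards Not Related when another cause is established. This has force: a sensible investigator would often reach a sensible answer. It is not a precedence rule, however. The section goes on to direct use of the two categories, and one of them is satisfied by timing whatever that weighing shows.

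The stakes are also limited. Relatedness is one descriptive item beside severity, frequency and expectedness. The protocol plans no test on it, and the 24-hour reporting of serious events in section 8.3.6 does not depend on it. This stands, and it limits the severity.

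Four stronger readings are tempting, and the document does not support them.

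- *Every on-study AE is Related.* This needs all 56 days to count as the intervention and any onset in that time to count as temporally related. The protocol says neither. The abstinence contingency runs for only 28 of those days, and the protocol allows for missed samples and withdrawal.
- *Any other possible cause makes an event Not Related.* The etiology must be established; a candidate cause is not enough.
- *The relatedness table cannot be interpreted.* A table can still be produced and read. Its weakness is that the split depends on the clause applied.
- *Events cannot be separated by phase.* The onset date is collected for each AE, so phase at onset can be derived. Even so, investigator attribution in a single-group study would not by itself show that the contingency caused harm.

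**Conclusion.** The point holds as a self-contradicting definition. As printed, the categories are not mutually exclusive: timing alone suffices for Related, an established alternate etiology or absence of a reasonable possibility alone suffices for Not Related, and nothing decides between them. The overlap covers 12 of 16 logical combinations, and every combination in which a temporal relationship and an established alternate etiology coexist. The share of actual AEs affected cannot be stated, because it depends on the events that occur and on what counts as the study intervention.

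The conclusion rests on reading 'or' as printed. It survives one looser reading and fails, for events with a temporal relationship, only if the three Not Related conditions are all required together. Severity is minor to moderate: this is a 20-participant, single-group proof-of-concept study that the protocol describes as minimal risk, and relatedness is reported descriptively. The definition is nevertheless wrong as written and feeds a planned safety table, so it is worth correcting before events are classified.

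**What to change.** Revise section 8.3.3.2 as follows.

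1. Make the categories exclusive. Related means that there is a reasonable possibility that the intervention caused the event; Not Related means that there is not.
2. Keep recognition of the event as a known effect of the intervention as support for Related, so that this category is not narrowed more than needed.
3. Treat timing and an established alternate etiology as factors weighed in that single judgement, and state that timing alone is not sufficient.
4. State what counts as the study intervention for this purpose: the whole system of sampling, prompts and payments, or the abstinence-contingent reinforcement of the B phase.
5. In section 9.3.4, tabulate phase at onset beside relatedness, derived from the onset date that section 8.3.5 already requires.

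The cost is a few sentences in the protocol and matching CRF help text. No new data are collected. Any events already classified would need to be reassessed under the revised wording so that the table uses one definition.

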8.3.3.3 EXPECTEDNESS

A provider with expertise in alcohol withdrawal syndrome will be responsible for determining whether an adverse event (AE) is expected or unexpected. An AE will be considered unexpected if the nature, severity, or frequency of the event is not consistent with the risk information previously described for the study procedures.

8.3.4 PERIOD AND FREQUENCY FOR EVENT ASSESSMENT AND FOLLOW-UP

The study coordinator will record events with start dates occurring any time after informed consent is obtained until seven (for non-serious AEs) or 30 days (for SAEs) after the last day of study participation. At each study visit, the investigator will inquire about the occurrence of AE/SAEs since the last visit. Events will be followed for outcome information until resolution or stabilization.

8.3.5 ADVERSE EVENT REPORTING

Investigators must report to the IRB as soon as possible, but in all cases within seven (7) working days after the reportable event had been made known to the investigator. All AEs occurring during the study must be documented on the relevant CRF pages. The following information should be documented for each AE:

- Description of the symptom event
- Classification of "serious" or "not serious"
- Severity
- Date of first occurrence and date of resolution (if applicable)
- Action was taken
- Causal relationship
- The outcome of the event (unknown, recovered, not yet recovered, recovered with sequelae, death)

8.3.6 SERIOUS ADVERSE EVENT REPORTING

The SAE form must be completed as thoroughly as possible with all available details of the event, signed by the investigator (or appropriately qualified designee), and emailed or faxed to medical monitor within 24 hours of first becoming aware of the event. Such SAE will be reported to the Ringful and, the WSU IRB within 24 hours of first becoming aware of the event.

9 STATISTICAL CONSIDERATIONS

9.1 SAMPLE SIZE DETERMINATION

This is a minimum viability proof of concept trial. The samples size is determined to provide preliminary usability data as required by an R41 project.

9.2 POPULATIONS FOR ANALYSES

The dataset will consist of all enrolled subjects. This excludes all patients who failed the screening for this study or those who are eligible but uninterested in study participation.

9.3 STATISTICAL ANALYSES

9.3.1 GENERAL APPROACH

Raw data will be entered directly into the Research Electronic Data Capture (REDCap) system on a secure server by research staff at baseline and all subsequent data from participants via cell phone will flow directly into REDCap.

First, we will perform generalized estimating equations for the repeated binary outcome of alcohol abstinence. This model will include the variables of 1) Time (individually varying timestamp from when the breath sample was submitted) and 2) Phase (A, B, A).

Second, we will analyze the outcome of 1) self-reported heavy drinking days (4+ standard drinks per drinking day for women, 5+ standard drinks per drinking day for men), 2) self-reported craving, and 3) self-reported craving, all over time.

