4 STUDY DESIGN

4.1 OVERALL DESIGN

This pilot study will utilize an A-B-A, completely within-subject design with the intent of recruiting twenty (n=20) total participants. During the first A phase, participants will receive reinforcement for simply submitting breath samples three times per day between 4 and 6 hours apart. In this application, we will utilize a Bluetooth enabled breathalyzer developed by BACtrack, but our smartphone-based technological solution will interact with any alcohol monitoring device, such as BACtrack Skyn. During the B phase, the delivery of reinforcers will be contingent upon the submission of an alcohol negative breath sample on an escalating schedule. The second A phase (i.e., return to the baseline phase) will involve the delivery of reinforcers for simply submitting a sample during the designated windows of time. We will also collect EMA data on stress, anxiety, depression, and other brief measures daily through their smartphone. Each phase will last a total of four weeks (i.e., two weeks of the first A phase, four weeks of the B phase, and then two more weeks of the A-phase) each for a total of 8 weeks of participation. To the extent possible, we will use existing protocols, procedures, and equipment that we have used in previous A-B-A studies.

This study will take place in Greater Inland Northwest area in cooperation with the Community Health Association of Spokane (CHAS) and other outpatient entities, community recruitment, etc. under the auspices of the WSU Program of Excellence in Addictions Research and the Analytics and PsychoPharmacology (APPL).

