9.3.5 BASELINE DESCRIPTIVE STATISTICS

We will initially run descriptive statistics across baseline variables to characterize the sample. All inferential results will be presented as point estimates with 95% confidence intervals, and we will use an alpha error rate of 0.05 as the threshold for statistical significance. Our approach is consistent with that of several similar RCTs involving tobacco smoking and alcohol use disorders.^{12,13,24,34-37}

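### The primary GEE on about 20 participants, at alpha 0.05 with 95% intervals, names no small-sample correction; run in its usual form it would exceed the stated 5% level

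*Protocol*

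**What the plan says.** Section 9.3.1 of the protocol names the primary method: "First, we will perform generalized estimating equations for the repeated binary outcome of alcohol abstinence". The model terms are the time stamp of each sample and the phase (A, B, A). Section 9.3.5 sets the inferential standard: results come as point estimates with 95% confidence intervals, and "we will use an alpha error rate of 0.05 as the threshold for statistical significance".

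The design in 4.1 is a "completely within-subject design with the intent of recruiting twenty (n=20) total participants". Each person contributes many observations: "participants will be asked to submit three breath samples daily for 8 weeks", split as "two weeks of the first A phase, four weeks of the B phase, and then two more weeks of the A-phase". For the analysis set, 9.2 says "The dataset will consist of all enrolled subjects".

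The protocol names no covariance estimator, working correlation, reference distribution, degrees of freedom or small-sample correction. It does not say that an uncorrected test will be used.

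**The concern.** GEE inference in its usual form takes standard errors from the sandwich estimator and compares the Wald statistic with 1.96. Both steps rely on a large number of independent clusters. Here the clusters are the participants, about 20. The long series of breath samples does not help, because the sandwich variance is built from one contribution per participant. With so few contributions it tends to be too small, and the normal reference ignores the uncertainty in it.

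The primary result is the effect of phase on abstinence. If the usual form is used, a nominal 5% test rejects too often and a nominal 95% interval covers too rarely, so the proof of concept would look firmer than it is. Section 10.1.2 lists demonstrated efficacy and a met primary endpoint among possible reasons to end the study, so the evidential standard may matter in practice.

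**Working it through.** **No figure to reproduce.** Section 9.1 sizes the trial for usability data and gives no power or precision calculation. The 0.05 is a nominal threshold, and its true level can be found only by supplying a variance estimator and reference distribution.

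**Inputs from the protocol.** Clusters n = 20 (4.1). Phases of 14, 28 and 14 days, so 56 days x 3 samples = 168 samples per person at most. Parameters p: intercept, Time and Phase give p = 4 if the two A phases are separate levels, or p = 3 if they share one. Alpha is 0.05, taken as two-sided to match the 95% intervals.

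**Closed-form check, with no assumption on abstinence.**
- Reference distribution alone: P(|t(n-p)| > 1.96). For p = 3, P(|t(17)| > 1.96) = 6.7%. For p = 4, P(|t(16)| > 1.96) = 6.8%.
- Adding sandwich shrinkage, approximated by a standard error too small by the factor sqrt((n-p)/n): for p = 3, 1.96 x sqrt(17/20) = 1.81, giving 8.8%. For p = 4, 1.96 x sqrt(16/20) = 1.75, giving 9.9%.

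**Null simulations at n = 20.** Three sets, each a GEE with Time and Phase and up to 168 samples per person, with no true phase effect. Assumptions that are not in the protocol:
- Set 1: 4,000 trials per setting; person SD 1.5, person-by-phase SD 0.7 (varied 0.3 to 1.0), day SD 0.7; independence working correlation.
- Set 2: 2,000 trials per setting; person SD 1, day-level AR(1) correlation 0.9, person-by-phase SD 0 or 0.5, 20% of samples missing at random; independence working correlation; Phase with two or three levels.
- Set 3: three-level Phase, with the negative rate varied.

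| Negative samples | Set | Ordinary sandwich, 1.96 | Mancl-DeRouen, t(n-p) |
|---|---|---|---|
| 70% | 2 | 6.8-8.1% | 3.9-5.2% |
| about 70% | 3 | 6.7% | 4.0% |
| 75-80% | 1 | 7.3% (6.9-7.8% over phase SD) | 3.4-4.5% |
| about 81% | 3 | 8.4% | 5.1% |
| 85% | 2 | 8.1-9.1% | 5.1-6.4% |
| about 93% | 3 | 11.7% | 7.7% |
| 95% | 2 | 13.5-14.1% | 9.5-10.5% |

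Monte Carlo standard error at 2,000 trials is sqrt(0.05 x 0.95 / 2000) = 0.5 percentage points at a 5% level, and sqrt(0.14 x 0.86 / 2000) = 0.8 points at 14%. In the set 2 settings, coverage of the nominal 95% interval is 100% minus the type I error, about 86-93%.

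**Is the number of clusters the cause?** In set 2 at 85% negative, the uncorrected test gives 8.1-9.1% with 20 participants, 6.5-7.2% with 50 and 5.0-5.5% with 200. The excess disappears as participants are added.

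**Are both parts of the correction needed?** In set 2 at 85% negative (three-level Phase, person-by-phase SD 0): uncorrected 9.1%; t reference only 7.1%; Mancl-DeRouen only 7.5%; both 5.9%. Each helps, and together they come closest to 5%.

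**Cost in precision.** Standard error x 1.053 and critical value 2.12 (t with 16 degrees of freedom) in place of 1.96: 1.053 x 2.12 / 1.96 = 1.14, an interval about 14% wider.

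**The case against.** The strongest objection is that the protocol states no error. It names GEE, alpha and the interval level, and a corrected covariance with a t reference is fully compatible with that text. The choice of variance estimator commonly sits in the SAP, which is not at hand. This stands in part. A reader might infer that the protocol fixes an uncorrected large-sample test; no sentence says so, and the inflation applies only if the usual form is used. What remains is that the protocol commits to a method, an error rate and a cluster count that do not fit together without a correction.

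The size is also open to challenge. The negative-sample rate drives the result and the protocol gives none. Excluding severe alcohol use disorder (5.2) makes a high rate plausible but does not establish one.

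Two further inferences are not supported. A reader might expect dropout to reduce the clusters to 16 or 12 and make matters worse. Section 9.2 keeps all enrolled subjects, so someone who leaves early remains a cluster with fewer samples, and no such loss is stated. A reader might also take B versus A on abstinence as the only inferential result. Section 9.3.1 also plans analyses of heavy drinking days and craving, and 9.3.5 applies its standard to all inferential results.

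Finally, this is a pilot sized for usability, and 7-8% against 5% is a modest excess. That limits the weight of the point. It does not remove it, since 9.3.5 still sets a significance threshold.

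**Conclusion.** The point holds in conditional form. With about 20 participants, GEE with the ordinary sandwich and a normal reference does not deliver the 5% level of 9.3.5. Type I error is about 7-8% at 70-80% negative samples and about 12-14% at 93-95%. The direction is secure: the closed-form check and all three simulation sets agree, and the excess vanishes with more clusters. The size is less certain, because it rests on assumed negative rates, between-person variation and within-person correlation, and because the protocol leaves the variance estimator open. The correction is not a complete cure: it gives roughly 4-6% at negative rates of 70-85%, but about 8-10% at 93-95%. The change is worth making, though the trial's validity does not turn on it.

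**What to change.** Unless the SAP already specifies this, add to 9.3.1: the GEE is clustered on participant, and standard errors, tests and 95% confidence intervals use a bias-corrected sandwich (for example Mancl-DeRouen) with a t reference on the number of participants minus the number of model parameters. Add that the correction brings the level near 5% at moderate abstinence rates but may leave about 8-10% if negative samples approach 95%, and that p-values will then be read cautiously.

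The model, its two terms and alpha stay as they are. The cost is a short addition to the text, a software option, and an interval about 14% wider at 20 participants.
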